4.11.10 Data Monitoring Committee

The study has a Data Monitoring Committee (DMC) to review periodically study progress and to review the blinded sample size re-estimation (BSSR, see Section 4.13.2) results as per the DMC Charter. The periodic reviews by the DMC include:

- screening, recruitment status, subject disposition
- safety status update of study
 - 1. TEAEs: severity, relationship, leading to discontinuation of study treatment
 - 2. SAEs and deaths
 - 3. Infusion-related reactions

Further details can be found in the DMC Charter.

4.12 Other Analyses

4.12.1 Analysis of Pharmacokinetic Endpoints / Variables

Plasma concentrations of rituximab will be listed and summarized for the PKS by treatment group and visit at which samples were taken. Descriptive statistics will include n, mean, median, min,max ,SD, CV%, geometric mean and geometric coefficient of variation.

Serum values below the lower limit of quantification (LLOQ) will be set to LLOQ/2.

A separate analysis plan for the Population PK modelling will be developed and results will be provided in a separate Population PK Report.

4.12.2 Analysis of Pharmacodynamic Endpoints / Variables

Pharmacodynamic endpoints / variables (see Section 3.2.3 for definitions) will be summarized by treatment group for the PDS.

Peripheral blood B-cell counts by time point will be summarized by treatment group:

- Descriptive statistics (including 95% CIs for means) for Emax.
- AUEC will be calculated using the linear trapezoidal rule. AUEC will be natural log transformed to obtain a point estimate as well as 90% and 95% CIs for the difference of arithmetic means using an ANOVA with study treatment and strata used in the stratified randomization as fixed effects. Point estimate and CIs will be re-transformed to the original scale to obtain point estimate and CIs for the ratio of geometric means.
- Time to B-cell depletion will be descriptively compared by Kaplan Meier curves and 95% CI for the median time to depletion in each treatment group. Subjects without a B-cell depletion will be censored at the date of their last B-cell count up to Week 28 for the Week 28 CSR, up to Week 52 for the Week 52 CSR, respectively.
- Time to B-cell repletion will be descriptively compared by Kaplan Meier curves and 95% CI for the median time to repletion in each treatment arm. Subjects without a B-cell repletion after a B-cell depletion will be censored at the date of their last B-cell count up to Week 28 for the Week 28 CSR, up to Week 52 for the Week 52 CSR, respectively.

A by-subject listing of pharmacodynamic data and endpoints will be provided.

[name] S.A Protocol RI-01-006

Statistical Analysis Plan

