9.3.5 Pharmacodynamic Analysis Population

The Pharmacodynamic Analysis Population will include all subjects in the PK and pharmacodynamic subset and sampled for pharmacodynamics who have at least an available

pre -dose pharmacodynamic sample and an available pharmacodynamic sample obtained after the administration of the first dose of rituximab has started.

Subjects will be considered included in the PK and pharmacodynamic subset if they participate in the PK and pharmacodynamic evaluations, have provided their written consent to participation and randomised to the study within the PK and pharmacodynamic subset.

Subject evaluability for specific parameters will be decided under blinded conditions.

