9.4.5 Pharmacodynamics Assessment

Peripheral blood B-cell counts will be comparatively evaluated for potential differences in parameters such as the area under the B-cell depletion-time curve (depletion AUEC).

Depletion is defined as Baseline (pre-dose at Visit 1) count minus the measured value.

The AUEC will be calculated using the linear trapezoidal rule. Only the values up to the last value below the individual subject baseline count will be included in the AUEC calculation.

Potential differences between DRL_RI and MabThera[®] in the AUEC will be investigated using a linear mixed-effects model with treatment as a fixed effect and subject as a random effect.

On the basis of B-cell counts a population pharmacodynamics evaluation including population pharmacokinetics-pharmacodynamics evaluation might be performed which will be evaluated in a separate analysis plan.

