2.3 Exploratory Objectives

Exploratory objectives are:

- To compare BOR up to Week 28 evaluated in accordance with the Lugano criteria (Cheson 2014⁴) in subjects with CD20-positive, LTB-FL treated with either DRL RI or MabThera®
- To explore the pharmacokinetic (PK) parameters of DRL RI and MabThera[®], using a population-PK modelling approach
- To explore the pharmacodynamic parameters of DRL RI and MabThera[®]. •

3 **INVESTIGATIONAL PLAN**

Overall Study Design and Plan 3.1

This is a Phase III, randomized, multicenter, double-blind, parallel-group study in subjects with previously untreated, Stage II-IV, CD20-positive, LTB-FL.

The study will enroll subjects with CD20-positive, LTB-FL who are asymptomatic for lymphoma specific B-symptoms. LTB-FL will be assessed according to the Groupe D'Etude des Lymphomes Folliculaires (GELF) criteria.³

Subjects will be randomized in a 1:1 ratio to one of the 2 study treatment groups:

- DRL RI
- MabThera®

Randomization will be stratified by

- CCI , see Section 4.10.1.6): low risk versus medium risk versus high risk
- tumor grade: 1-2 versus 3a
- geographical regions: United States of America (USA) versus Europe versus Asia Pacific.

The study drug DRL RI or MabThera[®] will be administered as an intravenous (i.v.) infusion, at a dose of 375 mg/m² of Body Surface Area (BSA), please see Section 4.7 for BSA formulas.

Subjects will receive induction treatment consisting of a weekly i.v. infusion for 4 weeks $(375 \text{ mg/m}^2 \text{ of})$ BSA) followed by maintenance treatment consisting of an i.v. infusion (375 mg/m² of BSA) every 8 weeks from Week 12 until Week 36, please see Figure 1 further below for study drug administration schedule.

Study will consist of:

- Screening: up to 35 days to assess & confirm study eligibility
- Treatment period: up to 36 weeks that includes both induction and maintenance periods. Subjects will attend study visits every week (± 2 days) during the Induction Treatment Period, Weeks 1 to 4 and at Week 8 (\pm 7 days). During maintenance treatment period subjects will attend the study visit at Week 12 ± 7 days, and thereafter every 8 weeks (± 7 days) until Week 36.
- Follow-up Period: subjects will be followed 52 weeks after the first dose of study drug (at Weeks • 44 and 52)

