3.2.3 Definition of Other Endpoints / Variables

Other endpoints / variables are:

- Pharmacokinetic (PK) parameters (e.g., clearance and volume of distribution) for DRL_RI and MabThera[®] derived by a population PK modelling approach (not covered by this SAP)
- Pharmacodynamic variables:
 - Emax: maximum post-dose depletion of B-cell counts, calculated as the maximum of the B-cell depletion-time curve defined as baseline (pre-dose at Visit 1) count minus post-baseline count
 - AUEC: area under the B-cell depletion-time curve up to the last value below or equal to the subject's baseline count prior to the subject's first count above the subject's baseline count (if there is any such value above the subject's baseline count)
 - Time to first B-cell depletion: time from date of randomization to the first occurrence of a value below the lower limit of quantification (for subjects with a baseline B-cell count below the lower limit of quantification, this endpoint is not defined)
 - Time to first B-cell repletion: time from the date of the first B-cell depletion (as defined above) to the subsequently first occurrence of a value above or equal to the lower limit of quantification (for subjects without a B-cell depletion, this endpoint is not defined).

[name] S.A Protocol RI-01-006

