4.4.5 Pharmacodynamic Analysis Set

The Pharmacodynamic Analysis Set (PDS) will include all subjects in the PK and pharmacodynamic subset and sampled for pharmacodynamics who have at least an available pre-dose pharmacodynamic sample and an available pharmacodynamic sample obtained after the administration of the first dose of rituximab has started. Subjects are included in the PK and pharmacodynamic subset if they consented and participated in the PK and pharmacodynamic evaluations.

Subject evaluability for specific pharmacodynamic parameters will be decided under blinded conditions.

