4.10.2.2 Sensitivity Analyses of the Primary Efficacy Endpoint / Variable

4.10.2.2.1 Stratified Analysis for Primary Efficacy Endpoint / Variable

Statistical Hypotheses

For the stratified analyses, the hypotheses will be as follow:

With

 $\pi_{\text{DRL}_\text{RI},j}$ denoting the true probability for BOR up to Week 28 in the DRL_RI treatment group in stratum j, $1 \le j \le 18$ (for the 18 strata used in the stratified randomization)

 $\pi_{\text{MabThera}^{\mathbb{B}},j}$ denoting the true probability for BOR up to Week 28 in the MabThera[®] treatment group in stratum j, $1 \le j \le 18$ (for the 18 strata used in the stratified randomization)

and $\delta = \pi_{\text{DRL}_\text{RI,j}} - \pi_{\text{MabThera}^{\circledast},j}$ denoting the common BOR up to Week 28 probability difference (common across the 18 strata used in the stratified randomization),

[name] S.A Protocol RI-01-006

the null hypothesis is

 $H_0: |\delta| \ge 0.17,$

verbally: DRL_RI is not biosimilar (is either inferior or superior) to MabThera[®] applying pre-specified symmetrical biosimilar margins $\pm 0.17 (\pm 17\%)$.

The alternative hypothesis is

 $H_A: |\delta| < 0.17,$

verbally: DRL_RI is biosimilar (is neither inferior nor superior) to MabThera[®] applying pre-specified symmetrical biosimilar margins ± 0.17 ($\pm 17\%$).

Statistical analysis method

Two-sided 90% and 95% CIs for the BOR up to Week 28 common probability difference between treatment groups (DRL_RI minus MabThera®) will be obtained using the stratified Mantel-Haenszel method^{10,11}, stratified by the strata used in the stratified randomization and implemented in SAS Proc FREQ. This analysis will be performed for the ITT analysis set.

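### The ln(AUEC) model for B-cell depletion omits the baseline B-cell count; the planned interval is valid but wider than it needs to be

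*SAP*

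**What the plan says.** Protocol 9.4.5 states: "Depletion is defined as Baseline (pre-dose at Visit 1) count minus the measured value". SAP 3.2.3 uses the same curve, "defined as baseline (pre-dose at Visit 1) count minus post-baseline count". AUEC is the area under it, stopped before the subject's first count above baseline. It is not divided by the baseline count or by the length of follow-up.

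SAP 4.12.2 log-transforms AUEC and obtains confidence intervals at the 90% and 95% levels "for the difference of arithmetic means using an ANOVA with study treatment and strata used in the stratified randomization as fixed effects", then back-transforms to a ratio of geometric means. The strata combine risk index, tumour grade and region; SAP 4.10.2.2.1 counts them ("for the 18 strata used in the stratified randomization"). Baseline B-cell count is not a stratification factor. SAP 4.14 describes the AUEC model with treatment only, and protocol 9.4.5 gives treatment as fixed and subject as random. None of the three has a baseline term.

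Under SAP 4.4.5, subjects in the PD Analysis Set must "have at least an available pre-dose pharmacodynamic sample". The PD objective is exploratory (SAP 2.3: "To explore the pharmacodynamic parameters of DRL RI and MabThera"). Protocol 4.1.1 puts the subset at about 90 subjects, about 45 per group.

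**The concern.** Baseline count is built into the endpoint. If depletion is near complete and lasts as long in everyone, a subject who starts with twice the B-cells has about twice the AUEC whichever product was given. On the log scale, ln(AUEC) is then close to ln(baseline) plus a term for how long the curve runs. The planned model leaves the whole ln(baseline) variance in the error term, except for any part that the strata explain.

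AUEC is the only PD comparison in this SAP that is based on a model. Population PK/PD modelling is optional and would fall under a separate plan. The stake is the width of the reported intervals for the ratio of geometric means. No trial conclusion depends on it.

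**Working it through.** The documents give no SD, power, margin or CI width for AUEC, so there is no planned figure to reproduce.

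**From the documents:** about 45 per arm; 18 strata; PD samples on Days 1, 8, 15 and 22 and at Weeks 12, 20, 28, 36, 44 and 52; linear trapezoidal rule.

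**Assumed:** lognormal baseline with CV 30-80%; near-complete depletion; 10-20% of curves ending at a random visit from Day 22 to Week 44; baseline unrelated to strata; identical products. The Day 1 end-of-infusion sample is left out.

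**Hand calculation**

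1. With full depletion from the first post-dose sample, ln(AUEC) = ln(baseline) + ln(effective duration). Write Vb and Vg for the two variances. The planned residual variance is Vb + Vg; with ln(baseline) in the model it is Vg. So narrowing = 1 - sqrt(Vg / (Vb + Vg)).
2. Vb = ln(1 + CV²): 0.0862 at CV 30%, 0.2231 at 50%, 0.4947 at 80%.
3. Take sampling days 0, 7, 14, 21, 84, 140, 196, 252, 308 and 364. Depletion is zero at day 0, so the first interval adds 7/2 = 3.5. A complete curve then has area 360.5 × baseline. A curve ending at one of the six visits from Day 22 to Week 44 has 17.5, 80.5, 136.5, 192.5, 248.5 or 304.5 × baseline.
4. The logs of these areas over 360.5 are -3.025, -1.499, -0.971, -0.627, -0.372 and -0.169. Their mean is -1.1107 and their mean square 2.1506.
5. For a proportion p of early ends, Vg = 2.1506p - (1.1107p)². This is 0.2151 - 0.0123 = 0.2027 (from unrounded terms) at p = 0.10, and 0.4301 - 0.0493 = 0.3808 at p = 0.20.
6. Narrowing of the log-scale CI:

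| Early ends | CV 30% | CV 50% | CV 80% |
|---|---|---|---|
| 10% | 16% | 31% | 46% |
| 20% | 10% | 21% | 34% |

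7. Example at CV 50% and 10% early ends. With 90 - 19 = 71 degrees of freedom, t = 1.667. Planned: 1.667 × sqrt(2 × 0.4258/45) = 0.229, a multiplicative half-width of ×1.26. With ln(baseline): 1.667 × sqrt(2 × 0.2027/45) = 0.158, or ×1.17.

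**Simulation** (1000 trials per setting; treatment plus 18 strata, with and without ln(baseline); allocation not balanced within strata; median residual count 1-10% of baseline; ranges over CV 30-80%)

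| Early ends | 90% half-width, planned | With ln(baseline) | Log-scale narrowing |
|---|---|---|---|
| none | ×1.12-1.36 | ×1.00-1.13 | 32-99% |
| 10% | ×1.22-1.42 | ×1.18-1.24 | 12-48% |
| 20% | ×1.29-1.48 | ×1.26-1.31 | 7-35% |

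Coverage of the planned 90% CI was 87-92%, so the planned interval is sound.

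**What shrinks or enlarges the gain**

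- Strata explain 30% of ln(baseline) variance: replace Vb by 0.7Vb in step 6. The gain becomes 12-39% with 10% early ends and 7-28% with 20%.
- 40% early ends: Vg = 0.8603 - 0.1974 = 0.6629. At CV 30% the gain is 1 - sqrt(0.6629/0.7491) = 6%.
- Incomplete depletion (median residual 30%): 1-38%. The low end, 1-8%, occurs when the residual varies independently from visit to visit.
- Other timings: about 3% if 20% of curves end during induction (SD of ln(baseline) 0.4), and about 80% if 10% end late with a Week 28 cut (SD 1.0).

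**The case against.** The strongest reply is that little follows from this. PD is exploratory, without margin, power statement or decision rule, and an ANOVA on treatment and strata is a legitimate pre-specified choice. That stands, and it limits the point to a free improvement.

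A second reply is that the size rests on inputs the documents do not supply: baseline spread, how complete depletion is, when curves end, and how far the strata already predict baseline. That also stands. The direction is secure where depletion is substantial; the percentage is illustrative and should be quoted only with its assumptions.

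Third, some of the plan is not visible. SAP 4.2.7 on combining strata is listed in the contents, but its text is not in the supplied copy, so fewer than 18 levels may be fitted. Runs with 6 or 12 levels gave the same direction.

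A reader might go further and infer that leaving out baseline biases the product comparison or invalidates its CI. The documents do not support that. Treatment is randomised, baseline is measured before dosing, and simulated coverage of the planned interval is near nominal.

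A reader might also think the covariate needs a substitution rule such as LLOQ/2 when baseline is zero or below the limit of quantification. It does not. Such a subject has no measurable depletion, so AUEC is zero and cannot be logged, whatever value the covariate takes. These subjects fall under the existing rule: "Subject evaluability for specific pharmacodynamic parameters will be decided under blinded conditions" (SAP 4.4.5; protocol 9.3.5 says the same: "Subject evaluability for specific parameters will be decided under blinded conditions").

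**Conclusion.** The point holds as one of precision only. The planned model omits a covariate that is part of the endpoint and is already measured in every subject of the PD set. Under the stated assumptions the log-scale 90% CI for the AUEC ratio would be roughly 7-48% narrower with ln(baseline) added. The benefit could be only a few percent if depletion is incomplete or many curves end very early, and larger than that range if curves are complete. The efficacy and safety conclusions are unaffected.

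**What to change.** In SAP 4.12.2, before unblinding, add ln(pre-dose Day 1 B-cell count) as a covariate in the ln(AUEC) model, alongside treatment and strata. It costs one model term and one degree of freedom and needs no new data. It does require a further SAP version, and the documents do not show whether there is still time for one before unblinding. A covariate added afterwards could look driven by the data.

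Separately, as an editorial correction, make the model described in SAP 4.14 (treatment only) match the one in SAP 4.12.2.

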4.12.3 Analysis of Data Related to the COVID -19 Pandemic

A summary of the number and percentage of subjects with visit impact and category due to COVID-19 pandemic will be presented by treatment group. Percentages will be based on ITT Analysis Set. A by-subject listing of visit impact and category due to COVID-19 pandemic will be provided.

COVID-19 laboratory test results will be summarized by visit and treatment group based on the ITT Analysis Set. A by-subject listing for COVID-19 laboratory test results as well as COVID-19 questionnaire will be provided.

4.13 Determination of Sample Size

4.13.1 Determination of Initial Sample Size

Published data for rituximab treatment versus a "watch and wait" strategy in the first line treatment of LTBFL (Ardeshna 2014^{Error! Reference source not found.}) revealed a treatment effect

4.13.2 Blinded Sample Size Re-Estimation

Due to the uncertainties regarding the assumed BORRs, a BSSR was planned and performed when BOR up to Week 28 was available for the first 50% of initially planned subjects. The sample size was reestimated on the basis of the observed pooled BORR to maintain statistical power of at least 80%. The same assumptions used in the initial sample size calculation were used except for the initially assumed BORRs. A reduction of sample size below the initial number of 250 subjects was not allowed. Full BSSR details are available in a separate BSSR SAP, especially a detailed BSSR algorithm and extensive simulations demonstrating maintenance of the type-I-error probability.

Based on the observed pooled BORR up to Week 28 and the same assumed difference as in the initial assumptions (Section 4.13.1), the revised total sample size obtained in the BSSR was 312 subjects (156 per group) to be randomized.

[name] S.A Protocol RI-01-006

Statistical Analysis Plan

4.14 Changes in the Conduct of the Study or Planned Analysis

In the protocol page 82, section 9.4.5 says that AUEC will be investigated using a linear mixed-effects model with treatment as a fixed effect and subject as a random effect.

However, as this is a parallel group study, AUEC will be analyzed using ANOVA with treatment as fixed effect.

The intercurrent events in statistical analysis plan are more specific and statistical methods for handling of intercurrent events are explained in detail.

Appendix 1 Schedule of Assessments

			Induction	Ireatment l	Period		Maintenance Treatment Period	Follow-	up Period
	2000aaaaa	Baseline		Week (Day) ± 2 days		Week ± 7 days	Week ± 7 days	Week ± 7 days	EOS/ET ¹ Week ± 7 days
Timing	Days -35 to -1	Days 0 to 12	2 (8)	3 (15)	4 (22)	00	12, 20, 28, 36	1	52
Baseline ³		×							
Informed consent ⁴	×								
Inclusion/exclusion criteria ⁵	×	×							
FLIP12 criteria	×								
Histological confirmation of diagnosis ⁶	×								
Medical, surgical and oncology history including medications	×								
Demographics	×								
Physical examination ⁷	×	×	×	×	×	×	×	×	×
Vital signs ⁶	×	×	×	×	×	×	×	×	×
Pregnancy test ⁹	×	x	×	×	×		×		×
ECOG performance status	×	×	x	x	×	x	×	x	x
Clinical laboratory tests ¹⁰	×	×	×	×	×	×	×	×	×
LDH and β-2 microglobulin	×	×	×	×	×	×	×	x	×
TB screening ¹¹	×								
Viral disease screening ¹²	×						X12	X12	X ¹²
12-Lead ECG	×								×
CT Scan ¹³ or [¹⁸ F]FDG-PET/PET- CT ¹⁴	×						X ^{13,14}		×
Bone marrow biopsy15	x						X ¹⁵		X ¹⁵
Randomisation		X ¹⁶							
Study drug administration ¹⁷		×	×	×	×		x		
PK sampling ¹⁸		x	×	×	×		X ¹⁸		
Pharmacodynamic sampling ¹⁹		×	×	×	×		\mathbf{X}^{19}	×	×
Immunogenicity ²⁰		×			×	×	X ²⁰	×	×
Adverse events including IRR	×	×	×	×	×	×	x	×	×
Concomitant medications	x	x	×	×	×	x	x	x	×
COVID-19 testing ²¹		×							
COVID-19 related screening questionnaire	×	×	×	×	×	x	×	×	×

Project Document Version No. 4.0 **Project Document Effective Date**: Date of last signature Page 55 of 65

CONFIDENTIAL

_

Parexel International
[name] S.A Protocol RI-01-006 Statistical Analysis Plan
Abbreviations: AE = adverse event; BAb = binding antibodies; COVID-19 = Coronavirus disease 2019; Ctrough = trough plasma concentration; CT = computed tomography; DNA = deoxyribonucleic acid; ECG = electrocardiogram; ECOG = Eastern Cooperative Oncology Group; EOS/ET = End of Study/Early Termination;[18F]FDG-PET: fluorine-18-fluorodeoxyglucose positron emission tomography; FL = follicular lymphoma; D : the provide the prov
¹ All subjects completing the study (Week 52) and those discontinuing the study at any time for any reason will attend the EOS Visit. Subjects experiencing disease progression will discontinue study drug and attend the ET Visit, which is to be scheduled 8 weeks after the last dose of study drug administration. These subjects will then be contacted by telephone for information on survival, AEs, and concomitant medications every 8 weeks, for a total observation period of 52 weeks. Subjects who wish to remain in the study but withdraw from the study drug for any reason other than disease progression will return for an ET Visit 8 weeks after the last dose of study drug and continue to attend scheduled tumour assessments (at which AE and concomitant medications every 8 weeks, for a total observation period of 52 weeks. Subjects who wish to remain in the study but withdraw from the study drug for any reason other than disease progression will also be collected) until disease progression or Week 52, whichever occurs first. Note: if these subjects subsequently experience disease progression then they will continue to be followed up by telephone every 8 weeks from that point of identification and for a total observation period of 52 weeks, as described for subjects discontinue to be followed up by telephone every 8 weeks from that point of identification and for a total observation period of 52 weeks, as described for subjects discontinue to be followed up by telephone every 8 weeks from that point of identification and for a total observation period of 52 weeks, as described for subjects discontinue of the tot disease progression.
this will be considered as Day 1 ³ If the assessment is repeated before dosing, then latest values/observations will be considered as baseline value/observation. ⁴ Informed consent must be obtained prior to undergoing any study-specific procedure. ⁵ All eligibility criteria must be met before a subject is randomised to study drug. Subjects that do not meet all requirements can be rescreened at the Investigator's discretion, following discussion with the Sponsor/designee Medical Monitor.
⁶ Subjects can be screened for the study based on a diagnosis of CD20-positive, low burden FL confirmed at the investigational site. Subjects must have sufficient tissue samples available for the central pathology review (obtained on or within 6 months prior to the screening date) and a centrally confirmed diagnosis prior to being randomised. ⁷ Complete physical examinations, including a thorough assessment of the Iymph nodes, liver, and spleen, will be conducted at Screening and at the EOS/ET Visit. Physical examinations at other study visits will be at the discretion of the Investigator, but should, at a minimum, include an assessment of the Iymph nodes, liver, and spleen, will be recorded at Screening and at the Homph nodes, liver, and spleen. Height will be recorded at Screening only. Weight will be recorded at each study drug dosing visit.
⁸ Temperature, blood pressure, pulse rate, and respiratory rate will be recorded at each time point. Vital signs will be monitored every 30 minutes during the course of the treatment administration and at end of infusion or more frequently as necessary. ⁹ Women of childbearing potential will have a serum pregnancy test during screening and a urine pregnancy test on Day 1 prior to randomisation, and all subsequent study drug dosing visits. A serum pregnancy test will be repeated at EOS/ET Visit. Additional pregnancy tests should be performed whenever pregnancy is suspected or at the discretion of the Investigator. All tests will be performed by the local laboratory according to local practice.
¹⁰ Clinical laboratory tests (haematology/coagulation/biochemistry/urinalysis) will be performed by local laboratories, prior to administration of study treatment. ¹¹ If latent TB is suspected based on clinical or epidemiological grounds, it should be further investigated using the tuberculosis testing as appropriate following local practice or investigator judgment.

Effective Date: 26 Nov 19

CONFIDENTIAL

49EC
0499D
28-253
581-8A
5DC-4{
1AA-B
D4A88
pe ID:
Envelo
ocuSign
ŏ

[name] S.A Protocol RI-01-006

Statistical Analysis Plan

- hepatitis B infection). Additional monitoring/management of subjects who were HCV antibody positive (and HCV RNA negative) at Screening should be done in accordance with ² Hepatitis B surface antigen, hepatitis B core antibody, HBV DNA (as applicable), HCV antibody, HCV RNA (as applicable), and human immunodeficiency virus to be conducted by local laboratory. HBV DNA at Screening, Week 12 and all visits from Week 12 onwards (only for subjects with history of hepatitis B or hepatitis B serology suggestive of past local practice and standard of care.
- be performed on the CT component of positron emission tomography computed tomography (PET-CT) scans with contrast if the quality of the CT part of PET-CT is equivalent to ¹³ Tumour assessments for the purpose of assessing subject eligibility (with central imaging confirmation) and medical care will be performed by the investigational site at Screening, the central imaging vendor for review and assessment of response for the primary and other efficacy endpoints. Disease assessments are to be performed as scheduled according to first administration of study drug may be used for determining study eligibility provided they are of adequate quality for subsequent central review. Tumour assessments may also that of a standard CT. The same modality (CT or PET-CT) should be consistently used throughout the study evaluations. All imaging performed for the study will be forwarded to Weeks 12, 28, and 52 (EOS/ET Visit) by reviewing CT scans (Neck, chest, abdomen, and pelvis) with contrast. Computed tomography scans obtained up to 4 weeks prior to the delays. Assessments are NOT to be scheduled based on the previous imaging time point, but rather Day 1 should be used as the Baseline when calculating when the on-study Table 1–1, regardless of treatment delays resulting from toxicity. Care must be taken in scheduling disease assessments to prevent the introduction of bias based on treatment tumour assessments are to be performed (with consideration of visit windows).
- ¹⁴ Fluorine-18-fluorodeoxyglucose positron emission tomography/computed tomography ([¹⁸F]FDG-PET or PET-CT) scan will be obtained where available (according to study site standard of care) at Screening. Weeks 12, 28, and 52 (EOS/ET Visit). Positron emission tomography scans acquired up to 6 weeks prior to Day 1 may be used for screening provided they are of adequate quality for subsequent central imaging review.
- subject who has a response of CR at an evaluation point and either had a bone marrow examination positive for FL at Screening or shows new abnormalities in the peripheral blood 15 Bone marrow biopsies or aspirations performed up to 6 weeks prior to the first administration of study drug may be used. Additional bone marrow biopsies are required for any counts or blood smear that clinically indicates a bone marrow evaluation is required.
- ¹⁶ All the baseline assessments must be reviewed by the investigators for final eligibility assessment before randomisation of the subject
- ¹⁷ The study drug proposed rituximab biosimilar [DRL_RI] or MabThera[®] will be administered as an i.v infusion, at a dose of 375 mg/m² of body surface area. Subjects will receive induction treatment consisting of weekly i.v infusions for 4 weeks followed by maintenance treatment consisting of an i.v infusion every 8 weeks up to Week 36. Subjects will be pre-medicated before each infusion with acetaminophen, diphenhydramine, and 100 mg i.v methylprednisolone or their equivalent to decrease the incidence and severity of acute IRRs. Randomisation in IWRS and administration of first dose of study medication should take place on the same day and this will be considered as Day 1.
 - ¹⁸ Only for the subjects identified for the PK and pharmacodynamic evaluation: one PK sample will be taken prior to initiation of infusion (pre-dose or C_{trough}) and a second sample immediately prior to the end of the infusion on Days 1, 8, 15, 22, and Week 12.
- ¹⁹ Only for the subjects identified for the PK and pharmacodynamic evaluation: separate pharmacodynamic samples will be taken prior to initiation of infusion (pre-dose) and immediately prior to the end of the infusion on Day 1, prior to the initiation of infusion of infusion on Days 8, 15, 22, and at Weeks 12, 20, 28, and 36. Samples will also be collected at the Week 44 and 52 visits.
- ²⁰ Samples for detection of BAb and NAb will be collected before the administration of study drug infusion on Day 1 and Day 22. Additional samples for detection of BAb and NAb will be collected prior to study drug infusion at Weeks 8 and 28, as well as at the visits of Week 44 and Week 52 (EOS/ET Visit).
- ²¹ COVID-19 testing (RT-PCR, Rapid Antigen test or test with similar nature antigen test but no antibody test) to be performed as close as possible but no more than 4 days before first dose administration. COVID-19 testing may be repeated at the discretion of the Investigator. Subjects should be randomised only after negative COVID-19 test result.

-8A28-2530A99D49EC	
AA-B5DC-4581	
e ID: D4A881	
n Envelope	
DocuSigi	

[name] S.A Protocol RI-01-006

Statistical Analysis Plan

